Appendix 4 Neuropsychiatric Inventory (NPI-Q) [41]

Scoring levels with example definitions for the NPI-Q

Frequency of occurrence (1~4)

1. Occasionally: less than once per week
2. Often: about once per week
3. Frequently: several times per week but less than every day
4. Very frequently: once or more per day

Severity of behavior (1~3)

1. Mild: mildly distressing to the patient and not a major problem
2. Moderate: distressing to the patient but easily overcome by reassurance
3. Marked: distressing to the patient and difficult to redirect or deal with

Distress to you (0~5)

0. Not at all
1. Minimally: rarely distressing and easily tolerated
2. Mildly: occasionally distressing, but not a significant problem
3. Moderately: somewhat distressing and problematic, but usually tolerable
4. Severely: very distressing and difficult to cope with
5. Very severely or extremely: markedly distressing and extremely difficult to cope with

The score for each item is calculated by multiplying the frequency by the intensity; and the total score for the NPI is calculated by adding the scores of all symptoms.

Thus, scores may range from 0 to a maximum of 144, where the higher the score, the more severe the psychopathology.

Summary table for NPI-Q scores.

Symptom		Frequency	Severity	Total (frequency × severity)	Distress to you
1. Delirium	Does the patient have a false idea, such as thinking that someone else has stolen his/her things? Do you suspect that someone is harming him?				
2. Hallucinations	Does the patient have hallucinations such as visual hallucinations or auditory hallucinations? See or hear something or sound that doesn't exist? Talking to someone who doesn't actually exist?				
3. Agitation/aggression	Does the patient often refuse help from others? Unmanageable? Stubborn? Shouting at others? Snoring others?				
4. Depression/dysphoria	Does the patient show grief or express a depression?				
5. Anxiety	Is it uncomfortable after the patient is separated from the caregiver? Does the patient have mental stress such as shortness of breath, sigh, can't relax or feel nervous?				
6. Joy/euphoria	Is the patient too happy and feeling too good? Feeling humorous and laughing at things that others are not interesting about? Joy that doesn't match the situation?				
7. Apathy	Did the patient lose interest in activities that were previously of interest? Indifferent to other people's activities and plans?				
8. Disinhibition	Does the patient lose self-control, such as talking to strangers like an acquaintance? Or talk regardless of the feelings of others?				
9. Irritability/lability	Does the patient show impatience or crazy behavior? Can't bear the delay? Can't wait patiently for the planned activities?				
10. Abnormal motor behaviour	Does the patient repeat nonsense activities, such as turning around a house, playing with buttons, bandaging with a rope, etc.? Or other repetitive activities?				
11. Sleep disorders	Does the patient wake others up at night? Get up early in the morning? Frequent snoring during the day?				
12. Eating disorders	Does the patient's weight decrease or increase? Do you like the taste of food changes?				
13. Total score					

Appendix 5 Hamilton Anxiety scale (HAMA) [42]

	Asymptomatic 0	Minor 1	Moderate 2	Heavier 3	Serious 4
1. Anxious mood	 ₀	 ₁	 ₂	 ₃	 ₄
2. nervous	 ₀	 ₁	 ₂	 ₃	 ₄
3. afraid	 ₀	 ₁	 ₂	 ₃	 ₄
4. insomnia	 ₀	 ₁	 ₂	 ₃	 ₄
5. memory, attention disorder	 ₀	 ₁	 ₂	 ₃	 ₄
6. depression mood	 ₀	 ₁	 ₂	 ₃	 ₄
7. somatic anxiety: the muscular system	 ₀	 ₁	 ₂	 ₃	 ₄
8. somatic anxiety: sensory system	 ₀	 ₁	 ₂	 ₃	 ₄
9. cardiovascular system symptoms	 ₀	 ₁	 ₂	 ₃	 ₄
10. respiratory symptoms	 ₀	 ₁	 ₂	 ₃	 ₄
11. gastrointestinal symptoms	 ₀	 ₁	 ₂	 ₃	 ₄
12. reproductive system symptoms	 ₀	 ₁	 ₂	 ₃	 ₄
13. autonomic nervous system symptoms	 ₀	 ₁	 ₂	 ₃	 ₄
14. performance at the time of the talks	 ₀	 ₁	 ₂	 ₃	 ₄
15. Total points	Score				

Appendix 6 Hamilton depression scale (HAMD) [45]

Item	0	1	2	3	4	score
1. Depressed Mood	No	Only tell when asked	Spontaneously expressed in conversation	The patient express this emotion from expressions, gestures, sounds or crying without words.	The patient's speech and non-verbal expressions (expressions, movements) are almost completely expressed as such emotions.	
2. Guilt	No	Blame yourself and feel that you have been hurting others	Think that you have committed a crime, or think twice about past mistakes and mistakes	Think that the current illness is a punishment for yourself, or that there is a crime of sin	Evil wants to be accused or threatening	
3. Suicide	No	He feels that living is meaningless.	Wishes he were dead, Often think of things related to death	Negative concept(Suicidal ideas)	Serious suicidal behavior	
4. Difficulty in falling asleep	No	Sometimes it is difficult to fall asleep, and still can't sleep for half an hour after going to bed.	Difficulty in falling asleep every night	/	/	
5. Sleep is not deep	No	Shallow sleep, nightmare	Woke up in the middle of the night (before 12 o'clock) (not including the toilet)	/	/	
6. Wake up early	No	Wake up early, wake up 1 hour earlier than usual, but can fall asleep again.	Can't fall asleep after waking up early.	/	/	
7. Work and Interests	Normal	Only tell when asked	Spontaneously, directly or indirectly, lose interest in activities, work, or learning, such as being slouched, hesitant, unable to persist or force himself to work or activity	Reduced activity time or reduced effectiveness, inpatients who participate in ward labor or entertainment for less than 3 hours a day.	Stop working because of the current illness, the residents can not complete the daily affairs of the ward without participating in any activities or without the help of others.	
8. Retardation: Slowness of thought, speech, and activity Apathy, Stupor	No	Slight retardation at interview	Obvious retardation at interview	Interview difficult	Complete stupor	
9. Agitation	No	feel a little uneasy when checking	Obviously uneasy or small movements	Can't sit still, stand up in the inspection	Pick up hands, bite fingers, pull hair, bite lips	
10. Mental anxiety	No	Only tell when asked	Spontaneously expressed in conversation	Expressions and words reveal obvious worries	Fears	

11. Somatic anxiety: dry mouth, bloating, diarrhea, snoring, abdominal cramps, palpitations, headaches, excessive ventilation and sighs, as well as frequent urination and sweating.	No	Mild	Moderate, with a positive appeal symptom	Severe, the above symptoms are serious, affecting life, need to be treated	Seriously affecting life and activities	
12. Gastrointestinal symptoms	Normal	Loss of appetite, but eat without the encouragement of others	Eating requires someone to urge or request, or need to apply laxatives or digestives	/	/	
13. Systemic symptoms	Normal	Four limbs, heavy back and neck, back pain, headache, muscle pain, general weakness	Significant symptoms	/	/	
14. Sexual symptoms: loss of libido, menstrual disorders, etc.	Normal	Mild	Severe	Not sure or not suitable for the test, not included in the total score		
15. Hypochondriasis	No	Self-absorption (bodily)	Preoccupation with health	Querulous attitude	Hypochondriacal delusions	
16. Loss of Weight	No	Weight loss of 1 kg or more in a week	Weight loss of more than 2 kg in a week			
17. Self-awareness	Yes	I know that I am sick, but I am poor at food, environment, work, etc.	Completely deny that there is a disease			
18 Total score	(Note: scores \leq 17 can be selected)					

Appendix 8 WHO-UCLA Verbal Learning Test [51]

Administration: I will give you some words of the object below. After I finish reading, please tell me the words you remember. You can say what you remember, not in order. Then I will give you a few more times. Please tell me every word you remember, including the words you have said before, and see how much you can remember at the end, ok?

The examiner clearly reads out at the speed of 1 second per word, records with Arabic numerals 1, 2, 3, etc., and records the number of insertions and the number of repetitions. Insertion of the same item twice or more is counted as one insertion, and each repetition is counted as one repetition, but the repetition of the inserted item is not counted as a repetition. Recall time every 2 minutes.

If the test has been carried out in the past 3 months, the date of the record check (year/month/day) // 0000/00/00 = not determined

project	1.1 first pass	2.1 second pass	3.1 third pass
arm			
cat			
ax			
bed			
aircraft			
ear			
dog			
hammer			
chair			
car			
eye			
horse			
knife			
bell			
bicycle			

The correct number	1.2	2.2	3.2
Insert word record	1.3	2.3	3.3
Number of insertions	1.4	2.4	3.4
Repeat number	1.5	2.5	3.5
Memory strategy	 1Yes  2No	 1Yes  2No	 1Yes  2No

4 the correct number	3 times correct total recall	(Abnormal reference value ≤ 18)
5 insert number	3 times the total number of inserts	
6 repeat number	Repeated recalls in 3 times	
7 Memory Strategy (According to object classification memory)	 1Yes	 2No

Delayed Recall

Administration: "Remember the words I have just read to you several times? Please remember as much as possible" (2 minutes of recall time. Record with 1, 2, 3 and other Arabic numerals, and record the number of insertions And the number of repetitions. The insertion of the same item multiple times is counted as one insertion, and each repetition is counted as one repetition, but the repetition of the inserted item is not counted as a repetition.)".

7.2	Correct number of recalls (reference value ≤ 6)	Correct number of recalls (reference value ≤ 6)
7.3	Insert word record	
7.4	Number of insertions	Number of insertions

7.5	Repeat number	Repeat number
7.6	Memory strategy (memory according to object classification)  1 Yes  0 No	

Cued Recall

Administration: The 15 words you have learned before can be divided into 5 categories. I will give you some tips below. Please continue to try to recall the words you have memorized. Record the picture "√".

Item category	8.1 Record		
Body class	 arm	 ears	 eyes
Animal	 cat	 dog	 horse
Tools	 Axe	 hammer	 knife
Furniture	 bed	 chair	 clock
Vehicle type	 Airplane	 car	 Bicycle

8.2	Measurable number	
-----	-------------------	--

[figure not shown]
Recognition

Administration: I will read 30 words below, among which I have just let you remember, some are added, please tell me which ones I let you remember and which ones are added. (Non-shadows are remembered - target words; shadows are interference items). For all words, just answer "yes" in the cell that is "yes" at the back, as long as the answer to "no" is snoring in the cell "No".

	Yes	No		Yes	No
mirror			lips		
hammer			tree		
knife			arm		
candle			nose		
motorcycle			sun		
ax			truck		
bell			eye		
chair			fish		
aircraft			ear		
tortoise			bicycle		
horse			snake		
thigh			Bench		
dog			bus		
table			bed		
Cat			car		

9.1	The number of non-shadowed "yes"	
9.2	The number of "yes" in the shadow	
9.3	9.1 minus 9.2	

Appendix 9 Rey-Osterrieth Complex Figure Test [52]

Administration: Please draw an identical picture according to the picture.

Scoring: Consider each of the 18 units separately (the highest score is 36 points). Appraise accuracy of each unit and relative position within the whole of the design. For each unit count as follows:

Correct	Placed properly	2 points
	Placed poorly	1 points
Distorted or incomplete but recognizable	Placed properly	1 points
	Placed poorly	0.5 points
Absent or not recognizable		0 points
1.	Cross upper left corner, outside of rectangle	 ₂  ₁  _{0.5}  ₀
2.	Large rectangle	 ₂  ₁  _{0.5}  ₀
3.	Diagonal cross	 ₂  ₁  _{0.5}  ₀
4.	Horizontal midline of (2)	 ₂  ₁  _{0.5}  ₀
5.	Vertical midline	 ₂  ₁  _{0.5}  ₀

6.	Small rectangle, within (2) to the left	 ₂  ₁  _{0.5}  ₀
7.	Small segment above (6)	 ₂  ₁  _{0.5}  ₀
8.	Four parallel lines within (2), upper left	 ₂  ₁  _{0.5}  ₀
9.	Triangle above (2), upper right	 ₂  ₁  _{0.5}  ₀
10.	Small vertical line within (2), below (9)	 ₂  ₁  _{0.5}  ₀
11.	Circle with three dots, within (2)	 ₂  ₁  _{0.5}  ₀
12.	Five parallel lines within (2) and crossing (3), lower right	 ₂  ₁  _{0.5}  ₀
13.	Sides of triangle attached to (2) on right	 ₂  ₁  _{0.5}  ₀
14.	Diamond attached to (13)	 ₂  ₁  _{0.5}  ₀
15.	Vertical line within triangle (13), parallel to the right side of (2)	 ₂  ₁  _{0.5}  ₀
16.	Horizontal line within (13), continuing (4) to the right	 ₂  ₁  _{0.5}  ₀
17.	Cross attached to (5), below (2)	 ₂  ₁  _{0.5}  ₀
18.	Square attached to (2), lower left	 ₂  ₁  _{0.5}  ₀
19. Total Score 		
		

Recall

Administration: Do you remember the picture I asked you to draw? Please remember and draw the picture as much as possible. If you can only recall some of the graphics, but can't determine their location, feel free to draw.

Correct	Placed properly	2 points
	Placed poorly	1 points
Distorted or incomplete but recognizable	Placed properly	1 points
	Placed poorly	0.5 points
Absent or not recognizable		0 points
1.	Cross upper left corner, outside of rectangle	 ₂  ₁  _{0.5}  ₀
2.	Large rectangle	 ₂  ₁  _{0.5}  ₀
3.	Diagonal cross	 ₂  ₁  _{0.5}  ₀
4.	Horizontal midline of (2)	 ₂  ₁  _{0.5}  ₀
5.	Vertical midline	 ₂  ₁  _{0.5}  ₀
6.	Small rectangle, within (2) to the left	 ₂  ₁  _{0.5}  ₀
7.	Small segment above (6)	 ₂  ₁  _{0.5}  ₀
8.	Four parallel lines within (2), upper left	 ₂  ₁  _{0.5}  ₀
9.	Triangle above (2), upper right	 ₂  ₁  _{0.5}  ₀
10.	Small vertical line within (2), below (9)	 ₂  ₁  _{0.5}  ₀
11.	Circle with three dots, within (2)	 ₂  ₁  _{0.5}  ₀
12.	Five parallel lines within (2) and crossing (3), lower right	 ₂  ₁  _{0.5}  ₀
13.	Sides of triangle attached to (2) on right	 ₂  ₁  _{0.5}  ₀

14.	Diamond attached to (13)	 ₂  ₁  _{0.5}  ₀
15.	Vertical line within triangle (13), parallel to the right side of (2)	 ₂  ₁  _{0.5}  ₀
16.	Horizontal line within (13), continuing (4) to the right	 ₂  ₁  _{0.5}  ₀
17.	Cross attached to (5), below (2)	 ₂  ₁  _{0.5}  ₀
18.	Square attached to (2), lower left	 ₂  ₁  _{0.5}  ₀
19. Total Score 		
		

Appendix 10 Digit Span Test (DST) [55]

Digit Span Forward

Administration: "Now we have to do a simple test, please pay attention to listen to me to read some numbers, I repeat it after I finish reading." Read a string of numbers at a rate of one digit per second. Test 1 is done first, and the number string of the same serial number in test 2 is repeated.

Scoring method: When both tests of the same length fail, and the test completes the highest score, the test ends. The highest score for success before the end of the record is the length of the digital breadth (any test in both tests of the same item is correct).

	Test 1		Test 2
3	5-8-2	3	6-9-4
4	6-4-3-9	4	7-2-8-6
5	4-2-7-3-1	5	7-5-8-3-6
6	6-1-9-4-7-3	6	3-9-2-4-8-7
7	5-9-1-7-4-2-8	7	4-1-7-9-3-8-6
8	5-8-1-9-2-6-4-7	8	3-8-2-9-5-1-7-4
9	2-7-5-8-6-2-5-8-4	9	7-1-3-9-4-2-5-6-8
10	5-2-7-4-9-1-3-7-4-6	10	4-7-2-5-9-1-6-2-5-3

Digit Span Forward length _____

Digit Span Backward

Administration: "I will say some numbers below, please listen carefully. After I finish reading, you repeat it again. I said 7-1-9, what should you say?" If the answer is correct, he said: "Here. and also". So from the second 3 digits of the test 1, if the answer is wrong or do not understand the practice, tell the correct answer should be 9-1-7, and another example, said: "Remember, to back." Another example is 3-4-8. If this success, it starts with 3 digits. If it fails again, it will return to the 2-digit test 1; if the subject passes the example, but the 3 digits are tested twice If it fails, it will return to 2 digits and the test will end.

Scoring method: When both tests fail, and the test completes the highest score, the test ends. The highest score for success is the length of the inverse digital breadth (any test in both tests of the same item can be successful).

	Test 1		Test 2
2	2-4	2	5-8
3	6-2-9	3	4-1-5
4	3-2-7-9	4	4-9-6-8
5	1-5-2-8-6	5	6-1-8-4-3
6	5-3-9-4-1-8	6	7-2-4-8-5-6
7	8-1-2-9-3-6-5	7	4-7-3-9-1-2-8
8	9-4-3-7-6-2-5-8	8	7-2-8-1-9-6-5-3

Digit Span Backward length _____

Appendix 11 Verbal Fluency Test (VFT) [57]

Animal Fluency

Administration: "Please tell as many animals as you know as soon as possible. The time is 1 minute. Are you ready? Start." Stop after one minute.

Scoring method: Record the name of the animal that was spoken within one minute of the subject. Mythical animals such as dragons, phoenixes, and unicorns are also correct. The names spoken by the subjects can be grouped by animal species (reference: mammals, birds, fish, insects, etc.), in tandem to the names of the animals listed in each subcategory, from the second of each subcategory. The animals start counting until they switch to another sub-category, and the sub-categories of each sub-category add the total number of series in this test. The number of conversions, that is, the number of times to switch between groups. Please note that duplicate, incorrect names, nicknames are not counted in the correct number, but are counted in the concatenation and conversion numbers.

1. animal _____
2. the correct number __
3. the number of repetitions __
4. the number of errors _ _

Vegetable fluency

Administration: "Please tell as many fruits as you can, as soon as possible. The time is 1 minute. Are you ready? Start." Stop after one minute.

Grading method: Record the name of the fruit spoken by the subject within one minute. The recording method is the same as above.

1. goods _____
2. the correct number __
3. the number of repetitions __
4. the number of errors __

Category Switching

Administration: "Please tell as many animals and fruits as you can as fast as possible. The time is 1 minute. Are you ready? Start." Stop after one minute.

Grading method: Record the number of item names spoken by the subject within one minute. The recording method is the same as above. Tandem is the name of the item listed consecutively in each sub-category, counting from the second item in each sub-category until it is converted to another sub-category, and the sub-series of each sub-category is added to obtain the total number of series in this test. . The number of conversions, that is, the number of times to switch between groups. Please note that duplicate, incorrect names, nicknames are not counted in the correct number, but are counted in the concatenation and conversion numbers.

1. article _____
2. the correct number __
3. the number of repetitions __
4. the number of errors __
5. the total number of series __
6. the number of conversions _ _

[figure not shown]
Appendix 12 Trail Making Test (TMT) [58]

Part A

Practice test

Administration: The following are some circles with numbers in the circle. I would like to ask you to connect in the order of 1-2-3... with a pen. Note: Do not leave the pen tip away from the paper and the line drawn must pass through the graphic. If I am wrong, I will point out that you need to go back and paint again. Let us give it a try now. The sooner you paint, the better. Are you ready? Start!

[figure not shown]
Note: The following is a practice test, not scored. Correct every time you make a mistake, and tell the correct connection method, while actively encouraging.

Actual test

Administration: There is a similar circle diagram here, please connect it again as above. Please note that the faster you draw, the better.

Do not leave the pen tip and the lines drawn must pass through the graphic. Start here (pointing to the starting point) until here (pointing to the end). Ready? Start. (time)

1.1 All digital completion time____(0-150) seconds (if 150 seconds is not completed, record 150)

[figure not shown]
1.2 Number of errors____(0-25; 88=Not applicable)

[figure not shown]
1.3 Correct number____(0-25; 88=Not applicable)

Part B

Administration: The following are 1-13 white circle numbers and 1-12 black circle numbers. They are also scattered. Please connect them in order, i.e. white circle 1 - black circle 1 - white circle 2 - black circle 2... Note: Do not leave the pen tip away from the paper and the line drawn must pass through the graphic. If I am wrong, I will point out that you need to go back and paint again. Let us give it a try now. The sooner you paint, the better. Are you ready? Start!

Practice test

2.1 All digital completion time _____(0-300) seconds (if 300 seconds is not completed, record 300)

2.2 Number Sequence Error Number _____(0-25; 88=Not applicable)

2.3 Correct number of lines _____(0-24; 88=Not applicable)

Appendix 13 Boston Naming Test (BNT) [59]

Administration: "I will show you some pictures now, please tell me what these pictures are."

If the tester fails to answer the answer, he is prompted: For example, "This is (plant), is there another name?"

If you still can't answer, then three answers are given in order to let the tester choose. Remember to record every answer of the testier, whether correct or not (only calculate the score of spontaneous naming: correct = 1, answer = 0).

	Picture	Answer (yes = 1; wrong = 0)	If wrong, specific record	If the answer is wrong, prompt	Answer (yes = 1; wrong = 0)	If wrong, specific record	If the prompt still answers the error, please select (circle the specific choice)		
1	2. Tree			plant			Peach blossom	Tree	Fireworks
2	3. Pen			Used for writing			straw	Original ball pen	pen
3	6. Scissors			tool			Scissors	clamp	Spoon
4	8. Flowers			plant			Vegetables	straw hat	flower
5	9. Saw			Woodworking equipment			Machine gun	Saw	Knife
6	12. Broom			Used for cleaning			Mop	Writing brush	Broom
7	*14. Mushroom			food			Mushroom	Cauliflower	umbrella
8	15. Hangers			Inside the wardrobe			roof	hanger	hook
9	16. Wheelchair			Patient use			Executive chair	trolley	wheelchair
10	17. Camel			animal			camel	mountain	Cattle
11	21 racquet			Sporting goods			Ping pong paddle	racquet	mirror
12	22. Snail			animal			snails	Squid	scallop
13	24. Seahorse			Marine life			hook	abalone	Seahorse
14	25. Darts			Used to throw			Target	Darts	rocket
15	30. Harmonica			Musical instrument			Harmonica	Air conditioner	box
16	31. Rhinoceros			animal			Canned knife	hippo	rhinoceros
17	33. Igloo			Used to live			Ice house	Grass house	grave
18	36. Cactus			plant			Iron tree	cactus	cross
19	37 escalator			Use up and down			Sliced bread	Slide	escalator
20	38. Harp			Musical instrument			harp	floor lamp	piano
21	42. Stethoscope			Doctor			Earphone	Stethoscope	sphygmomanometer
22	43. Pyramid			In Egypt			Zongzi	Sphinx	pyramid
23	46. Funnel			Pour water			Funnel	Ice cream cones	Pump
24	47. Accordion			Musical instrument			Harmonica	accordion	Blinds
25	50. Compass			painting			Cotton pliers	ruler	Compasses
26	52. Tripod			For photography			tripod	Mechanical arm	easel
27	54. tongs			Appliance			Spatula	tongs	canoe
28	57. Flower shed/ trellis			Park has			Flower shed/ trellis	trash can	network
29	59. Protractor			stationery			Pound scale	Triangle ruler	Protractor
30	60. Abacus			Counting			Calculator	Abacus	Curtain
Total	31			32			33		

Appendix 14 Activities of daily living (ADL) [60]

Ask the insider to rate the following functions of the patient based on the information provided (assessed according to the level of intelligence).

Rating	Instrumental Daily Living Ability Scale (LADH) Scoring Project
1	Ability to use the phone
	 1、 take the initiative to operate the phone - check the number, dial, etc.
	 2、 can dial a few familiar numbers
	 3、 can answer the phone but not dial the phone
	 4、 cannot use the telephone
2	Shopping
	 1、 independently handle all shopping needs
	 2、 a small amount of shopping independently
	 3、 need to accompany on any purchase
	 4、 completely unable to shopping
3	Cooking
	 1、 independently plan, prepare and make the right amount of meal
	 2、 if the raw materials can be prepared to prepare enough meal
	 3、 heating, serving or cooking, or cooking but not keeping the right amount
	 4、 Need to prepare the meal and do it well
4	Hosting housework
	 1、 independently host housework or occasionally need help (such as heavy work needs family help)
	 2、 do daily light physical housework such as washing dishes, making beds
	 3、 do daily light physical housework but cannot maintain an acceptable level of cleanliness
	 4、 all housework needs help
	 5、 do not participate in any housework
5	Washing
	 1、 can complete a personal bath
	 2、 wash small pieces of clothing - wash socks, etc.

	 3、 all washing must be done by others
6	Transportation
	 1、 independent public transport or driving a car
	 2、 travel by taxi, but no bus
	 3、 take the bus when accompanied by others
	 4、 can only travel by taxi or car with the help of others
	 5、 no travel at all
7	Responsibility for the medical care
	 1、 can take medicine seriously according to the correct time and dose
	 2、 if you prepare for each dose, you can take medicine
	 3、 you can't prepare your own medicine
8	Financial ability
	 1、 independently handle finance (budget, write checks, pay rent, bills, go to the bank), collect and maintain income channels
	 2、 manage daily shopping, but need help in banking affairs and big shopping, etc.
	 3、 can't handle finance

9 IADL total score

Rating	Somatic Self-care Ability Scale (PSUS) Scoring Project
10	Bowel and bladder function at the toilet,
	 1、 in the bathroom can be completely self-care, no incontinence
	 2、 need to be reminded of self-cleaning, or need help, or a small number of accidents (at least once a week)
	 3、 dirty or wet during sleep, more than once a week
	 4、 dirty or wet when awake, more than once a week
	 5、 incontinence
11	Eating
	 1、 no need to help when eating
	 2、 eating a small amount of time to eat and/or need to prepare special food, or need help after cleaning after meals
	 3、 need moderate help for meal, and it is not neat

	 4、 all meals need a lot of help
	 5、 can't eat at all, and resist feeding by others
12	Dressing
	 1、 wear clothes, undress, and choose clothes from your wardrobe
	 2、 wearing clothes and undressing, need a small amount of help
	 3、 need moderate help in dressing and choosing clothes
	 4、 need more help in wearing clothes, but with the help of others
	 5、 can't wear clothes at all, and it is against the help of others
13	Carding (tidy, hair, nails, hands, face, clothes)
	 1、 always dressed neatly, properly decorated, no need to help
	 2、 can properly decorate themselves, occasionally need a small amount of help, such as repairing beard
	 3、 need moderate or reasonable help or guidance in combing
	 4、 all combing matters need help, but can be kept neat after others help
	 5、 actively oppose the efforts of others to help sort out
14	Walking
	 1、 walk to the venue or urban area
	 2、 Walk in the residential area or walk near a street
	 3、 walking needs help (choose 1) a() cane, b() walker, c() wheelchair
	 1-In and out without help
	 2-In and out need help
	 4、 don't need to sit in a chair or a wheelchair, but you can't push it yourself without help
	 5、 more than half of the time bedridden
15	Bathing
	 1、 take a bath (bath, shower, bath), no need to help
	 2、 need help when getting in and out of the tub
	 3、 only wash your face and hands, cannot wash other parts of the body

	 4、 cannot take a bath, but with others to bathe him
	 5、 cannot take a bath, and resist efforts to keep him clean

16 BADL total score_____

17 ADL total score (IADL+BADL)_____

The total score below 16 is completely normal, and greater than 16 points have different degrees of functional decline, up to 64 points.

The single item is divided into 1 normal, 2 to 4 is divided into functional decline, where there are 2 or more than ≥ 3 points, or the

total score is ≥ 22 points, there are obvious obstacles to function.

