7.2.13 Activities of daily living (ADL) [60] (Appendix 14)

The ADL scale can evaluate the daily activities of the subject comprehensively, accurately and quickly. It consists of the physical life self-care scale and the instrumental ADL. There are 14 items, including two parts: first, the physical life self-care scale has a total of 6 items, including toilet, eating, dressing, grooming, walking and bathing; second, instrumental ADL has a total of 8 items, including call, shop, prepare meals, do housework, laundry, use transportation, take medicine and financing abilities. The higher the subject scores, the worse the ability of daily living.

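### Appendix 14 ADL item 5 should rate laundry, but its normal level describes bathing, so lost laundry ability can score as normal; the levels of items 10 and 14 also need correcting (minor)

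*Protocol*

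**What the plan says.** Section 7.2.13 describes the scale: "There are 14 items, including two parts", six for self-care and eight instrumental. The instrumental activities are "call, shop, prepare meals, do housework, laundry, use transportation, take medicine and financing abilities". Bathing is listed among the self-care activities.

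Appendix 14 prints the answer levels.

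- **Item 5 (headed Washing).** Level 1 is "can complete a personal bath". Level 2 concerns small pieces of clothing. Level 3 is "all washing must be done by others". Bathing has its own entry as item 15.
- **Item 10 (toilet).** Level 1 requires full self-care without incontinence. Level 2 includes "a small number of accidents (at least once a week" (the form then closes the bracket). Level 3 is "dirty or wet during sleep, more than once a week". Level 4 gives the same frequency while awake.
- **Item 14 (walking).** Level 4 is "don't need to sit in a chair or a wheelchair, but you can't push it yourself without help".

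The note below the form treats a total under 16 as normal and a total above 16 as some degree of decline. It treats a single item scored 2 to 4 as decline. It finds marked impairment when two or more items score at least 3 or the total is at least 22.

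**The concern.** The normal level of item 5 describes a different activity from the one the item is meant to measure. No level describes doing all of one's own laundry. A rater who follows the printed line gives the normal score to anyone who still bathes alone, whatever has happened to their laundry. Bathing then counts in two items and laundry may count in none.

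Item 10 has a separate fault. A frequency floor with no upper limit at level 2 contains the frequency printed at levels 3 and 4, so one pattern of accidents can meet two levels. Item 14 level 4 says that no chair is needed and also that the person cannot propel it.

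The ADL is collected at baseline (section 6.5) and at every in-person follow-up (section 6.6). Section 4.4 names daily living ability in asymptomatic mutation carriers as something to be followed over time. An instrumental item that can miss real decline matters most for that purpose.

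**Working it through.** **Inputs.** There are 14 items (7.2.13), and 1 is the normal score on each (note to Appendix 14). The levels of items 5 and 10 and the cut-offs of 16 and 22 are taken as printed in Appendix 14.

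**The form's own figure.** The note gives a maximum total of 64. Summing the highest printed level of each item gives:

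- instrumental: 4+4+4+5+3+5+3+3 = 31
- self-care: 6 × 5 = 30
- total: 31 + 30 = 61

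The stated maximum is therefore not reproduced. That is a separate discrepancy, and nothing below depends on it.

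**Item 5.** Take a person who bathes unaided, has all laundry done by others, and is normal on the other 13 items.

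- Level 1 ticked, because the person bathes alone: 13 × 1 + 1 = 14. This is the lowest possible total and is under 16.
- Level 3 ticked, because the item rates laundry: 13 × 1 + 3 = 16.

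The difference is 2 points. A total of exactly 16 is neither below nor above 16, so the form's sentence on the total does not classify it. The single-item rule would mark the 3 as decline. With level 1 ticked, nothing on the form shows any loss.

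If washing in level 3 is read to include bathing, this person does not meet level 3 either. The score is then 1 and the loss is certain to be hidden.

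**Item 10.** Take the other 13 items as normal.

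| Level ticked on item 10 | Total |
|---|---|
| 2 | 13 + 2 = 15 |
| 3 (during sleep) | 13 + 3 = 16 |
| 4 (while awake) | 13 + 4 = 17 |

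Moving between the overlapping levels changes the total by 1 (15 to 16) or 2 (15 to 17). The opening words of level 2 and the order of the levels show that it was meant as the rarer category. The bracketed frequency says otherwise.

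**Item 14.** There is no numerical effect to compute. The two halves of level 4 cannot both be true.

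**Both items together.** Take a person who bathes alone, has all laundry done by others, is wet during sleep twice a week, and is normal on the other 12 items.

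| Item 5 | Item 10 | Total | Items at 3 or more |
|---|---|---|---|
| 1 | 2 | 12 + 1 + 2 = 15 | 0 |
| 1 | 3 | 12 + 1 + 3 = 16 | 1 |
| 3 | 2 | 12 + 3 + 2 = 17 | 1 |
| 3 | 3 | 12 + 3 + 3 = 18 | 2 |

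If item 5 rated laundry throughout and the item 10 levels were exclusive, only the last row would remain.

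**Where the cut-offs are used.** The eligibility criteria (6.2 and 6.3), the visit intervals (Table 1 in 6.6) and the analyses in section 8 do not refer to any ADL total or cut-off.

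**The case against.** The last table invites a stronger reading: that the form classes the same patient as normal or as markedly impaired, depending on the rater. The documents do not support that as the finding, for three reasons.

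- It needs both ambiguities in one constructed record, with everything else normal.
- Being wet in sleep twice a week matches item 10 level 3 almost word for word, so a rater has little reason to tick level 2.
- The 15-point record is not cleanly normal, because the single-item rule already calls a score of 2 a decline.

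A reader might also infer from item 10 that the form adds noise at the transition from asymptomatic to symptomatic. That is weak. The CDR table in Appendix 15 places frequent incontinence at its severe level, and section 6.3 excludes severe dementia that would interfere with assessment.

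The wording may also be a translation fault. The appendices show other signs of one: grooming is headed Carding in Appendix 14, and the vegetable fluency task in Appendix 11 asks for fruits. The forms in use at the sites are not shown and may be correct. Section 10.2 also provides central rater training and unified scoring.

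These arguments limit the size of the point and make item 10 secondary. They do not remove the item 5 fault, because section 7.2.13 and the printed form contradict each other within the protocol. Training on a form that names the wrong activity does not correct it.

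**Conclusion.** The point holds as a minor one. Item 5 level 1 contradicts section 7.2.13 and can score lost laundry ability as normal, which lowers an otherwise normal total from 16 to 14. Item 10 level 2 overlaps levels 3 and 4, with an effect of 1 to 2 points, although the intended order can be inferred. Item 14 level 4 contradicts itself, with no computed effect.

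The consequence is limited to ADL scores and functional description. Nothing in the protocol makes eligibility, visit timing or a stated analysis depend on the cut-offs. The sizes assume that the levels are applied as printed and that all other items are normal. Whether any collected data are affected depends on the wording of the site-language forms, which the protocol does not show. The swing from 15 to 18 is arithmetically possible but should not be presented as the expected effect.

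**What to change.** 1. Reword Appendix 14 item 5 level 1 so that it rates doing one's own laundry, as section 7.2.13 requires.
2. Reconcile item 10 level 2 and item 14 level 4 with the source version of the instrument, so that the levels of each item are mutually exclusive and consistent. The replacement wording should come from that source.
3. Check the site-language forms for the same three faults.
4. Only if those forms carry the error, run one sensitivity analysis of the ADL total without items 5 and 10. Treat it as a continuous score and do not apply the cut-offs of 16 and 22, which belong to the 14-item total. Do not flag every record with item 5 scored 1, because that is the normal answer and would mark nearly every unimpaired participant.

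The cost is three corrected lines, a check of the site forms and at most one extra analysis. The downside is that, if site forms change, scores before and after the change are not strictly comparable on the corrected items.
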